Figure 2	Study design overview dose-escalation safety lead-in healthy subjects Groups 1-4a/b	10
Figure 3	Study design overview PoP in subjects with a recent S. aureus SSTI.	13
Figure 4	Sequence for evaluating both efficacy objectives in order to control the overall type I error below 7.5% (one-sided) and the power equal to 80%	.31

CONFIDENTIAL 208833 (STAPH AUREUS BIOCONJ-001 STG) Statistical Analysis Plan Amendment 5

LIST OF ABBREVIATIONS

AE	Adverse event
CI	Confidence Interval
CRF	Case Report Form
EAP	Exploratory Analysis Plan
ES	Exposed Set
FAS	Full Analysis Set
FDA	Food and Drug Administration
GCP	Good Clinical Practice
GSK	GlaxoSmithKline
HR	Hazard Ratio
ICF	Informed Consent Form
CCI	
iSRC	Internal Safety Review Committee
LL	Lower Limit of the confidence interval
MedDRA	Medical Dictionary for Regulatory Activities
mFAS	Modified Full Analysis Set
NA	Not Applicable
PD	Protocol Deviation
pIMD	Potential Immune-Mediated Disease
PoP	Proof of Principle
PPS	Per-Protocol Set
SAE	Serious adverse event
SAP	Statistical Analysis Plan
SBIR	GSK Biological's Internet Randomisation System
SD	Standard Deviation
SRT	Safety Review Team
SSTI	Skin and Soft Tissue Infection
TFL	Tables Figures and Listings
TOC	Table of Content
UL	Upper Limit of the confidence interval
ULN	Upper Limit of the Normal range

1. DOCUMENT HISTORY

Date	Description	Protocol Version
04 JUN 2020	First version	Version 01, dated 03 JUN 2020
03 JUN 2021	Amendment 1 (alignment to protocol amendment and other minor changes)	Amendment 02, dated 02 APR 2021
11 MAR 2022	Amendment 2 (alignment to protocol amendment and other minor changes)	Amendment 04, dated 30 NOV 2021
30 MAY 2022	Amendment 3 (Modifications in interim analysis SAS codes and operational procedure)	Amendment 04, dated 30 NOV 2021
17 OCT 2022	Amendment 4 (alignment to protocol amendment 6 and addition of elimination codes)	Amendment 06, dated 06 OCT 2022
31 Jul 2023	°CCI	Amendment 06, dated 06 OCT 2022

To evaluate vaccine efficacy (VE) in the prevention of recurrent culture confirmed S. aureus SSTIs compared to placebo	 Rey secondary endpoint: Number of subjects with at least one culture confirmed case of recurrent S. aureus SSTI starting from Day 75 (i.e. 14 days after the second dose) up to 12 months after the second dose Secondary endpoint: Number of subjects with at least one culture confirmed case of recurrent S. aureus SSTI starting from Day 15 (i.e. 14 days after the first dose) up to 12 months after the second dose 	

Source: Modified from Table 10 of STAPH AUREUS BIOCONJ-001 STG protocol amendment 2, dated 02 April 2021 AE = Adverse Event; pIMD = potential Immune-Mediated Disease; SAE = Serious Adverse Event; SSTI = Skin and Soft Tissue Infection; VE = Vaccine Efficacy;

3. STUDY DESIGN

The study is divided in two phases: a first dose-escalation safety lead-in phase and then a Proof of Principle (PoP) phase. Figure 1 presents a high-level overview of the whole study design. More detailed figures are provided in the respective subsections for dose-escalation safety lead-in (Figure 2) and PoP (Figure 3).

208833 (STAPH AUREUS BIOCONJ-001 STG) Statistical Analysis Plan Amendment 5

adj = adjuvanted Grp = Group a/b = vaccine/placebo Rando = Randomisation SE = Safety evaluation by SRT/ iSRC chair (blinded review) or iSRC (unblinded review) PoP = Proof of Principle

Dose-scalation safety lead-in healthy subjects

Figure 2 Study design overview dose-escalation safety lead-in healthy subjects Groups 1-4a/b

208833 (STAPH AUREUS BIOCONJ-001 STG) Statistical Analysis Plan Amendment 5

CDISC is not calculating with Day 0, i.e. interval between Day –1 and Day 1 is 1 day.

Grp = Group

a/b = vaccine/placebo

adj = adjuvanted

Rando = Randomisation

SE = Safety evaluation by SRT/ iSRC chair (blinded review) or iSRC (unblinded review) for details refer to Section 8.6.6 in the Study Protocol

PoP = Proof of Principle

M = Month

V = Vaccination

BS-S = Blood Sample for Safety evaluation

- Vaccination schedule(s):
 - **Group 1 Half dose non-adjuvanted** (first group), 2 parallel groups:
 - **Group 1a Half dose non-adj**.: 1 dose of Sa-5Ag half dose, non-adjuvanted at Day 1
 - Group 1b Placebo: 1 dose of placebo (saline) at Day 1
 - Group 2 Full dose non-adjuvanted (second group), 2 parallel groups:
 - **Group 2a Full dose non-adj**.: 1 dose of Sa-5Ag full dose, non-adjuvanted at Day 1
 - Group 2b Placebo: 1 dose of placebo (saline) at Day 1
 - **Group 3 Half dose adjuvanted** (third group), 2 parallel groups:
 - Group 3a Half dose adj.: 1 dose of Sa-5Ag half dose, adjuvanted at Day 1
 - Group 3b Placebo: 1 dose of placebo (saline) at Day 1
 - **Group 4 Full dose adjuvanted** (fourth group), 2 parallel groups:
 - **Group 4a Full dose adj**.: A series of 2 doses of Sa-5Ag full dose, adjuvanted (*S. aureus* candidate vaccine, target vaccine formulation) given approximately 2 months apart (Days 1 and 61)
 - **Group 4b Placebo:** A series of 2 doses of placebo (saline) given approximately 2 months apart (Days 1 and 61)

• Safety monitoring:

For each group in the dose-escalation safety lead-in, a staggered enrolment of 8 subjects is planned as follows: 1 vaccinated subject + 1 subject receiving placebo (sentinel subjects) followed by 5 vaccinated subjects + 1 subject receiving placebo after safety assessment of safety data collected up to Day 8. The 2 sentinel subjects in each group should be vaccinated on 2 different days.

The fourth group (Full dose adjuvanted) will receive a second vaccine/placebo dose with an interval of approximately 2 months and subjects of all the groups will be followed until study end (i.e. for 12 months after last vaccination for each subject).

The investigator is not permitted to start the administration of Dose 1 for the next group and Dose 2 in the fourth group until receipt of the favourable outcome of the safety evaluation.

During the whole study period, if the investigator becomes aware of a holding rule being met, he/she will suspend vaccination and will inform GSK immediately (e.g. in case of death or any life-threatening SAEs). Please, refer to section 8.6 of the study protocol for detailed description of holding rules and safety monitoring.

208833 (STAPH AUREUS BIOCONJ-001 STG) Statistical Analysis Plan Amendment 5

PoP in subjects with recent S. aureus SSTI

Figure 3 Study design overview PoP in subjects with a recent S. aureus SSTI

Note: CDISC is not calculating with Day 0, i.e. interval between Day -30 and Day 1 is 30 days.

208833 (STAPH AUREUS BIOCONJ-001 STG) Statistical Analysis Plan Amendment 5

a/b = vaccine/placebo SE = Safety evaluation by iSRC (unblinded), for details refer to Section 8.6.6 in the Study Protocol PoP = Proof of Principle SSTI = Skin and Soft Tissue Infection Rando = Randomization Vac = Vaccine Plac = Placebo M = Month V = Vaccination

BS-S = Blood Sample for Safety evaluation

• Vaccination schedule(s):

- **Group 5a Vaccine:** A series of 2 doses of *S. aureus* candidate vaccine (Sa-5Ag full dose adjuvanted) given approximately 2 months apart (Days 1 and 61)
- **Group 5b Placebo:** A series of 2 doses of placebo (saline) given approximately 2 months apart (Days 1 and 61)

• Safety monitoring:

The enrolment and vaccination in the PoP phase will also follow a staggered approach. After safety assessment of the first vaccination of the first approximately 40 subjects (randomised with a 3:1 ratio either to the GSK *S. aureus* candidate vaccine or to the placebo group) the full enrolment of the remaining subjects in the PoP phase will continue. The remaining subjects will be randomised with a 1:1 ratio either to the GSK *S. aureus* candidate vaccine or to the glacebo group.

Safety of the subjects in the PoP vaccination epoch will be monitored for the entire duration of the study with an overall duration of participation for each subject of approximately 14 months (i.e. 12 months after last vaccination).

For both, PoP staggered enrolment/vaccination and the PoP full enrolment/vaccination, the investigator is not permitted to start the administration of Dose 1 for the next group and Dose 2 until receipt of the favourable outcome of the safety evaluation.

During the whole study period, if the investigator becomes aware of a holding rule being met, he/she will suspend vaccination and will inform GSK immediately (e.g. in case of death or any life-threatening SAEs). Please, refer to section 8.6 of the study protocol for detailed description of holding rules and safety monitoring.

4. ANALYSIS SETS

4.1. Definition

Table 2Definition of the analysis sets

Analysis Set	Description
Screened	All subjects who were screened for eligibility
Enrolled	All subjects who entered the study (who were randomized or received study intervention or underwent a post-screening study procedure). The allocation in a group will be done in function of the randomized intervention; non-randomized subjects will be part of a "Non randomized" group. Note: screening failures (who never passed screening even if rescreened) and subjects screened but never enrolled into the study (met eligibility but ultimately not enrolled) are excluded from the Enrolled analysis set as they did not enter the study.
Exposed	All subjects who received at least 1 dose of the study treatment. The allocation in a group is done in function of the administered treatment.
Full Analysis Set (FAS)	All subjects who received at least 1 dose of the study treatment and have post- vaccination efficacy data
Modified Full Analysis Set (mFAS)	All subjects who received full study treatment course to which they are randomised and have post-vaccination efficacy data

Analysis Set	Description	
Per Protocol (PP)	All subjects who received full study treatment course to which they are randomised and have post-vaccination efficacy data (mFAS) minus subjects with protocol deviations that lead to exclusion from PP	
Unsolicited Safety	All subjects who received at least 1 dose of the study treatment (Exposed Set) that report unsolicited AEs/report not having unsolicited AEs	
Solicited Safety	All subjects who received at least 1 dose of the study treatment (Exposed Set) who have solicited safety data in the period beginning 30 minutes after vaccination until 7 days after the vaccination.	
Solicited Safety 30m	All subjects who received at least 1 dose of the study treatment (Exposed Set) who have solicited safety data during a period of 30 minutes after the vaccination	
Overall Safety Set	All subjects who received at least 1 dose of the study treatment (Exposed Set) who have solicited safety data including 30 minutes after vaccination and during a period of 7 days from the vaccination and/or report unsolicited AEs/report not having unsolicited AEs	

4.2. Criteria for eliminating data from Analysis Sets

Elimination codes are used to identify subjects to be eliminated from analysis. Detail is provided below for each set.

4.2.1. Elimination from Exposed Set (ES)

Table 3Elimination codes from ES

Code	Condition under which the code is used	Visit (timepoints) where the code is applicable
800	Fraudulent data	All
900	Invalid informed consent	All
1030	Study vaccine not administered at all	All

4.2.2. Elimination from Full Analysis Set (FAS)

All the elimination codes used for the ES are applicable and in addition the code:

- 1500a (Drop out before 14 days after first vaccination of the PoP phase)
- 1501a (No drainage sample for culture collected for recurrence of SSTI post first vaccination-PoP phase)

4.2.3. Elimination from modified Full Analysis Set (mFAS)

All the elimination codes used for the ES are applicable and in addition the codes:

- 1500b (Drop out before 14 days after second vaccination of the PoP phase)
- 1501b (No drainage sample for culture collected for recurrence of SSTI post second vaccination-PoP phase)
- 1070a (Incomplete treatment course).

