# 10.2. Populations for analyses

| Analysis Set                         | Description   |
|--------------------------------------|---|
| Screened                             | All subjects who were screened for eligibility  |
| Enrolled                             | All subjects who entered the study (who were randomized or received study intervention or underwent a post-screening study procedure). The allocation in a group will be done in function of the randomized intervention; non-randomized subjects will be part of a "Non randomized" group. Note: screening failures (who never passed screening even if rescreened) and subjects screened but never enrolled into the study (met eligibility but ultimately not enrolled) are excluded from the Enrolled analysis set as they did not enter the study. |
| Exposed                              | All subjects who received at least 1 dose of the study treatment. The allocation in a group is done in function of the administered treatment.  |
| Full Analysis Set (FAS)              | All subjects who received at least 1 dose of the study treatment and have post-
vaccination efficacy/ immunogenicity data  |
| Modified Full Analysis Set
(mFAS) | All subjects who received full study treatment course to which they are randomised and have post-vaccination efficacy/immunogenicity data   |
| Per-Protocol (PP)                    | All subjects who received full study treatment course to which they are randomised
and have post-vaccination data (mFAS) minus subjects with protocol deviations
that lead to exclusion from PP   |
| Unsolicited Safety                   | All subjects who received at least 1 dose of the study treatment (Exposed Set) that report unsolicited AEs/report not having unsolicited Aes  |
| Solicited Safety                     | All subjects who received at least 1 dose of the study treatment (Exposed Set) who have solicited safety data in the period beginning 30 minutes after vaccination until 7 days after vaccination.  |
| Solicited Safety 30m                 | All subjects who received at least 1 dose of the study treatment (Exposed Set) who have solicited safety data during a period of 30 minutes after the vaccination.  |

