4.2.4. Elimination from Per-protocol analysis Set (PPS)

All the elimination codes used for the mFAS are applicable and in addition the codes reported in the Table below.

Table 4Elimination codes from PPS

Code	Condition under which the code is used	Visit (timepoints) where the code is applicable
1040	Administration of concomitant vaccine(s) forbidden in the protocol	All
1050	Randomisation failure (e.g., subject assigned to wrong stratum, subject randomized out of order)	All
1060	Randomisation code was broken (study blinding/unblinding procedures)	All
1070	 Study treatment not administered per protocol: wrong route; correct treatment administered but not compatible with treatment regimen associated to treatment schedule; wrong treatment/replacement administered; 	All
	 wrong treatment repracement administered, treatment administered with a Staph aureus infection ongoing Study treatment not prepared as per protocol (e.g. reconstitution) 	
1080	Vaccine temperature deviation	All
1090	Expired vaccine administered	All
2010	Eligibility criteria not met	All
2040	Administration of concomitant medication(s) forbidden in the protocol	All
2050	Not withdrawn after developing withdrawal criteria other than prohibited concomitant vaccination/medication – forbidden medical condition	All
2060	Not withdrawn after developing withdrawal criteria other than prohibited concomitant vaccination/medication infection related to the vaccine	All
2080	Subjects did not comply with the vaccination schedule	All

Code	Condition under which the code is used	Visit (timepoints) where the code is applicable
2120	Obvious incoherence, abnormal serology evolution or error in data (incoherence between CRF and results, wrong sample labelling)	All
2130	testing performed on samples not aligned with ICF; Subjects bled but not supposed to be bled	All

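### SAP codes 1501a and 1501b remove subjects from the two confirmatory efficacy sets because an SSTI recurrence was not sampled, so set membership depends on the outcome

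*SAP*

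**What the plan says.** SAP 4.2 makes the codes act on people, not on visits or episodes: "Elimination codes are used to identify subjects to be eliminated from analysis". For the FAS, SAP 4.2.2 adds "1501a (No drainage sample for culture collected for recurrence of SSTI post first vaccination-PoP phase"). For the mFAS, SAP 4.2.3 says "All the elimination codes used for the ES are applicable and in addition the codes", and these include "1501b (No drainage sample for culture collected for recurrence of SSTI post second vaccination-PoP phase"). SAP 4.2.4 carries the second code into the per-protocol set: "All the elimination codes used for the mFAS are applicable and in addition the codes reported in the Table below".

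SAP Table 5 and protocol 10.3.3.1 assign the mFAS to the key secondary test and the FAS to the co-secondary test.

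The set definitions do not mention a drainage sample. SAP Table 2 defines the mFAS as "All subjects who received full study treatment course to which they are randomised and have post-vaccination efficacy data"; protocol 10.2 has "All subjects who received full study treatment course to which they are randomised and have post-vaccination efficacy/immunogenicity data". Neither document defines efficacy data. The endpoint is "Number of subjects with at least one culture confirmed case of recurrent" *S. aureus* SSTI (SAP section 2), and SAP 5.3.1 expects several cases in some subjects.

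Protocol 5.2.2 and 8.4.2.1 plan a drainage sample at every recurrence. Protocol 8.3 requires it only where feasible and classes a case without microbiological testing as a suspected recurrence. SAP section 8 lists no change from the planned analyses.

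**The concern.** A subject without a recurrence can never receive 1501a or 1501b. The codes therefore select on the outcome, and if the vaccine works they can remove more placebo than vaccine subjects. The protocol gives an untested case a category; the SAP removes the person. Because efficacy data is undefined, this is an unstated condition rather than a flat contradiction.

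Three further problems follow from the wording.

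1. **Any or all recurrences.** The visible text does not say which is meant. Read literally, a subject with one confirmed and one unsampled recurrence is removed together with the confirmed case.
2. **Window.** 1501b runs from the second dose, but the endpoint counts cases from 14 days later. An unsampled episode on Day 61 to 74 removes the subject. A sampled one is not counted, but the subject stays.
3. **Nesting.** 1501a is not an mFAS code. A subject with an unsampled episode between doses can be outside the FAS but inside the mFAS. A later confirmed case would then count in the key test but not in the co-secondary test, although the co-secondary window contains the key window.

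In addition, SAP 7.1 and 7.3 set the 13- and 27-event triggers without saying that the cases must be in the analysed set, so triggered and analysed counts can differ.

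**Working it through.** **Design inputs** (protocol 10.1.1 and 10.1.2, SAP 7.2): hazard ratio 0.39, one-sided alpha 7.5%, power 80%, looks at 13 and 27 events, interim alpha 1.613%, non-binding futility.

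**Reproducing the plan.** θ = ln(1/0.39) = 0.942. A fixed design needs 4(1.440 + 0.842)²/0.942² ≈ 23.5 events. Two looks with O'Brien-Fleming alpha and beta boundaries need 26.4, rounded up to 27. At 48% information the alpha split is 1.613% and 5.887%. The stated design reproduces.

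**Assumptions.** 0.07 is read as the placebo risk of a confirmed case over the 351-day key window. The unsampled share of recurrences is 10 to 30%. Within-subject clustering is a gamma frailty with variance 0 to 4. The documents give none of these except the 0.07.

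**Subjects removed, no clustering.** The placebo confirmed rate is −ln(0.93) = 0.0726. The unsampled rate is 0.0726 × (1 − c)/c, where c is the sampled share.

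- c = 0.9: 0.0081 placebo and, × 0.39, 0.0031 vaccine; 0.8% and 0.3% of subjects removed.
- c = 0.7: 0.0311 and 0.0121; 3.1% and 1.2% removed.

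With variance 4 the upper ends rise to 3.3% and 1.4%.

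**Confirmed events lost, literal reading.** At 0.39 the 27 events split about 19.3 placebo and 7.7 vaccine.

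- c = 0.9: 19.3 × 0.0080 + 7.7 × 0.0031 = 0.18.
- c = 0.7: 19.3 × 0.0306 + 7.7 × 0.0121 = 0.68.

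Simulation with 2,000,000 subjects per arm gives 0.18, 0.36 and 0.86 (10% unsampled) and 0.69, 1.32 and 3.09 (30% unsampled) for variance 0, 1 and 4. If the code reaches only subjects without a confirmed case, no event is lost.

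**Rate ratios from the same simulation**

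| Scenario | Keep at risk | Remove if any unsampled | Remove only if no confirmed case | Censor at episode |
|---|---|---|---|---|
| True 0.39, 30% unsampled, variance 0 | 0.391 | 0.391 | 0.384 | 0.391 |
| True 0.39, 30% unsampled, variance 4 | 0.421 | 0.451 | 0.416 | 0.434 |
| True 0.39, sampled 90% placebo, 70% vaccine | 0.303 | 0.303 | 0.304 | 0.303 |
| True 1, sampled 90% placebo, 70% vaccine | 0.777 | 0.776 | 0.789 | 0.777 |

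With equal sampling at the null, all four stay within 0.01 of 1. The unequal-sampling rows are essentially the ratio of sampled shares (0.7/0.9 = 0.778), whatever is done with the subjects.

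**Power if events are lost.** Two looks, drift θ√d/2, futility ignored. A final critical value of 1.483 keeps the overall 7.5%. Power is 83.7% at 27 events, 82.5% at 26, 81.3% at 25 and 80.0% at 24. If 5.89% is used as the nominal final level: 81.7%, 80.5%, 79.2% and 77.8%.

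**Log-rank check** (600 subjects, one look, one-sided 5.89%, 8,000 replicates; removed against kept):

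- 0.39, equal sampling, no clustering: power 80.8% and 80.8% at 10% unsampled; 80.1% and 81.0% at 30%.
- 0.39, variance 3, 30% unsampled: 67.4% and 74.2%.
- Null, equal sampling, no clustering: rejection 5.9% and 5.7% at 10%; 5.9% and 6.0% at 30%.
- Null, variance 3, unsampled 30% vaccine and 10% placebo: rejection 22.0% and 18.9%.

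**Sensitivity of a 27-event result.** With z = (placebo − vaccine)/√total, a 9 against 18 split gives 9/√27 = 1.73, p = 0.042. Losing two placebo cases gives 7/√25 = 1.40, p = 0.081.

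**Window gap.** Per 300 placebo subjects over 14 days, at the key-window rate: 300 × 0.0726 × 14/351 = 0.87 confirmed cases, so 0.1 to 0.4 unsampled. At the rate implied by 0.12 − 0.07 = 0.05 over about Day 15 to 75: 300 × 0.05 × 14/60 = 3.5, so 0.4 to 1.5.

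**Nesting.** Per 300 placebo subjects, the number in the mFAS but not the FAS runs from 300 × 0.05 × 46/60 × 0.111 = 1.3 (Day 15 to 60, 10% unsampled) to 300 × 0.05 × 0.429 = 6.4 (Day 1 to 60, 30%; 6.3 by simulation). Of these, 0.1 to 1.6 would have a key-endpoint case.

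**The case against.** The strongest reply is that 1501b simply puts the efficacy-data condition into operation. A subject with a confirmed case has a sample and has efficacy data, so the code should reach only subjects with no cultured case, and then no event is lost and the rate ratio moves by at most 0.007. That reading is reasonable, but the visible text does not state it, and set membership would still depend on the outcome.

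Several other points have weight:

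- The protocol plans a sample at every recurrence, so the unsampled share may be below 10%. Evaluators are blinded, so there is no specific reason to expect a large difference by arm.
- Even the extreme corner leaves about 24 events, where two-look power is 80.0%, the target. The 77.8% arises only if 5.89% is used as a nominal level, which is a separate question.
- The 7-point power loss comes from a fixed 600 subjects and an assumed variance of 3, whereas the trial is event-driven. The 9 against 16 example was chosen so that both lost cases are placebo.
- SAP 7.2 speaks of samples of 13 and 27 cases, which suggests analysed cases. The trigger point is therefore one of clarity.
- Part of the SAP efficacy section is blacked out and may contain handling rules.

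These points bear on size and on side issues. They do not change what SAP 4.2.2 and 4.2.3 say.

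**Conclusion.** The concern holds. As written, both confirmatory comparisons exclude subjects on a post-randomisation outcome, under a condition that the set definitions do not state. It should be fixed.

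The effect is probably small, but that is a judgement and not a bound, since neither the unsampled share nor the repeat-recurrence rate is given. With equal sampling and independent recurrences, removal changes power by about 1 point or less and the hazard ratio by about 0.001. A material loss needs the literal reading together with strong clustering and about 30% unsampled; the rate ratio then moves toward 1. With unequal sampling and clustering, about 3 points of null rejection come from the codes (22.0% against 18.9%). The rest comes from the culture-confirmed endpoint and remains after the codes are deleted.

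**What to change.** - Remove 1501a and 1501b from the FAS and mFAS; keep them for the per-protocol set only if wanted.
- Keep these subjects in the analysis and count only culture-confirmed cases as events.
- Pre-specify one handling of an unsampled episode, either continued at risk or censored at that episode, and use the other as a sensitivity analysis. Reconcile the choice with the censoring rule in SAP Table 5, which refers to SSTI cases without saying confirmed.
- State that the 13- and 27-event triggers count cases in the analysed set.
- Add an analysis of confirmed plus suspected recurrences, unless the blacked-out text or the Exploratory Analysis Plan already has one. This is the analysis that addresses unequal sampling.

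If the codes stay, define whether any or all recurrences are meant, set the window, give a confirmed case precedence, and explain why the FAS and mFAS are not nested. Copying 1501a into the mFAS would deal with the nesting but would widen the outcome-dependent exclusion, so removal is preferable.

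The cost is SAP wording and a little extra analysis. No new data are needed.
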